## **1.0 BACKGROUND AND RATIONALE**

Currently there is no evidence supporting the optimal timing for the post-op MRI imaging in patients with extradural spine tumors. The goal of that imaging is to get the optimal image quality for the evaluation of the degree of resection of spine tumors, in order to guide further therapy as indicated. The current practice is based on brain tumor literature and involves MRI within 72 hours after surgery {Albert, 1994 #9}. The drawbacks of this practice are potentially suboptimal image quality, presence of peri-operative changes that resolve over time and do not represent neoplastic disease, patient discomfort associated with early postoperative pain and need to be positioned in the scanner for a certain time, difficulties arranging the scans within the time constraints.

### *Hypothesis:*

The working hypothesis is that MR imaging 2 to 3 weeks after surgery is no worse in quality and utility than immediately postoperatively (within 72 hours).

### *Background and significance:*

The current standard of care in the management of the extradural spinal tumors is a multidisciplinary approach involving medical, surgical and radiation oncology teams.

In case of extradural spinal tumors, the goals of surgery are either extensive local disease debulking, decompression of neurological elements and/or creation of a tumor-free zone between the spinal cord and tumor (separation surgery) to allow subsequent stereotactic radiosurgery (SRS).

Stereotactic radiosurgery is a relatively new and rapidly developing method that allows curative as well as long term palliative control of primary and metastatic tumors. It is a form of radiotherapy which can be highly effective not only in radiosensitive tumors, like breast cancer, but also in tumors resistant to conventional radiotherapy, like renal cell carcinoma {Balagamwala, 2012 #12; Gerszten, 2007 #14; Gerszten, 2005 #13}. SRS is typically scheduled two-to-four weeks after the surgical procedure.

Planning phase of SRS includes imaging of the surgical bed in the form of MRI so as to delineate the precise area to be radiated. This is required in order to give maximum radiation to the tumor tissue and at the same time minimizing normal tissue irradiation (spinal cord and nerves), which can have debilitating side effects. MRI allows to distinguish normal from pathologic tissue, but the MRI picture in the post-operative period is confounded due to the presence of surgical perturbation leading to edema, blood and serum collection in the early phase and neovascularization later. Optimal timing for postoperative MRI that allows best quality images is currently unknown. Current protocol utilized by our multidisciplinary spine tumor team is based on the earlier reports from brain. According to it, MRI is obtained within 48 – 72 hours postoperatively.

Several studies have been done to find an optimal timing of imaging, especially MRI in the last 2 decades, which have shown that the imaging in the first 72 hours is essential to collect information in order to plan postoperative radiotherapy {Albert, 1994 #9}. These findings have been formulated as Canadian recommendations in the treatment of glioblastoma multiforme {Mason, 2007 #3}. However a recent study on tumor bed dynamics in brain metastasis has supported obtaining MRI as close to SRS as possible {Jarvis, 2012 #10}. There is no literature to support timing for MRI in spinal column tumors.

## **2.0 OBJECTIVES**

### *Study Design:*

This is a prospective diagnostic study for which no standard of care currently exists.

### *Primary aim:*

Assess if Magnetic Resonance Imaging (MRI) at 2 to 3 weeks after surgery (aka: later imaging) leads to the same clinical decisions and has the same probability of being chosen by a physician for guiding the subsequent management of the patient, compared with immediately postoperative MRI (within 72 hours, aka: early imaging).

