### *Secondary aims:*

Investigate the differences between early and late MRI by comparing:

Size of tumor in three dimensions;

Extent of edema;

Presence and extent of fluid collection;

Spine Oncology Study Group score;

Involvement of adjacent levels;

Progression of tumor;

Patient's preference/performance scale right after each image had taken: level of discomfort (measured by visual analog scale) at around the time (within 48 hours) each MRI was performed.

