### *Sample:*

Patients admitted to Cleveland Clinic for surgical management of metastatic extradural spinal tumors will be considered for the study. We anticipate the initial enrollment of 8 patients, which is a number chosen arbitrary for the pilot study. Based on results of this study we will perform power analysis and determine the number of subjects needed to get statistically significant results. Inclusion will not depend in any way on age, gender, ethnicity, or any other personal characteristics other than clinical relevance. We expect the study population to be similar to the spine surgery population seen at the Cleveland Clinic for neoplastic pathologies.

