### **5.0 RESEARCH PLAN**

#### *Imaging protocol:*

We will identify the patients meeting the above criteria and consent them for the study. Another MRI will be obtained 2-3 weeks postoperatively. The routine spine MRI protocol will be utilized, which includes the following sequences: haste localizer, sagittal T1, T2, and STIR, axial T2 for lumbar spine or axial gradient echo for cervical and thoracic spine, axial T1, post contrast sagittal and axial T1. All scans will be obtained using a 1.5 Tesla magnet. When indicated, sedation or anxiolysis and IV hydration for low glomerular filtration rate will be administered by radiology per protocol.

*Image analysis:*

The image acquisition dates will be blinded and the images independently reviewed by two neuroradiologists, a radiation oncologist, and a spine surgeon. Each of them will compare and choose a better-quality image. These results will be compared and inter-observer variability will be established.

Radiology (2 independent neuro-radiologists) will be blinded to all quantitative data (including the date of post-op MRI) and they will be asked to evaluate the following parameters:

- a. Level(s) of surgery = number ie L3, L4
- b. Presence of hardware = Y or N
- c. Does hardware obscure canal = Y or N
- d. Nature of surgery = 0 separation surgery/decompression only, 1 corpectomy, 2 combination of 0+1
- e. Fluid collection = AP\*Lateral\*CC in CM
- f. Epidural disease pre op = SOSG grading system AND max thickness at N level
- g. Epidural disease post op = SOSG grading system AND max thickness at N level
- h. Nature of marrow replacement (preop and residual on post op) = 1-4 for 25%, 50%, 75%, and 100% replaced respectively
- i. Compression fracture pre and post = Y or N
- j. Adjacent level involvement pre and post = Y or N

Spine surgeon and radiation oncologist will be blinded to date and use a scale of

- a. 0 = not confident,
- b. 1 = confident
- c. 2 = very confident

in terms of confidence in contouring/tumor targeting using a particular image set

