## **8.0 STATISTICAL CONSIDERATIONS**

Power analysis was not performed for this pilot study, since magnitude of differences is unknown. Obtained data will be used for designing a larger study. Kappa statistics will be calculated to evaluate the inter-rater reliability for the primary aim. For the secondary aims, descriptive statistics will be used.

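### The primary aim asks whether early and later MRI lead to the same clinical decisions, but no decision is recorded per image set and the only primary-aim statistic is agreement between readers

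*Combined protocol and SAP*

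**What the plan says.** Section 2.0 (Primary aim) has two parts, both contrasting later with early MRI in the same patient: whether later MRI "leads to the same clinical decisions and has the same probability of being chosen by a physician for guiding the subsequent management". The hypothesis in section 1.0 is also framed as a comparison of scans and names utility separately from quality.

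Section 5.0 (Image analysis) lists what readers record:

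- All four readers make a paired choice: "Each of them will compare and choose a better-quality image". The stated use follows: "These results will be compared and inter-observer variability will be established".
- The two neuroradiologists complete items a to j, which describe the surgery and the imaging findings.
- The spine surgeon and the radiation oncologist give a 0–2 score "in terms of confidence in contouring/tumor targeting using a particular image set".

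The table in section 6.0 adds only the MRI time points.

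Section 8.0 gives the whole analysis in two sentences: "Kappa statistics will be calculated to evaluate the inter-rater reliability for the primary aim" and "For the secondary aims, descriptive statistics will be used". The secondary aims do set the scans against each other ("Investigate the differences between early and late MRI by comparing"), but the items listed are imaging findings and patient discomfort.

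**The concern.** The aim, the data items and the statistic do not line up. The aim concerns scans: does the decision or the choice change with timing? The statistic concerns readers: do they agree with each other?

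For the decision half there is no variable to analyse. The nearest is the 0–2 score, a weak proxy, because a reader can give the top score to both sets and still decide differently from each. No analysis is named for that score.

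For the choice half there is a usable proxy, but it concerns image quality rather than use in management, and the only planned use is comparison between observers.

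At stake is what the pilot can report. Section 2.0 (Sample) says: "Based on results of this study we will perform power analysis and determine the number of subjects needed". A larger study could take early/late estimates of imaging findings from this pilot, but none of decision agreement. A high kappa, or equal confidence scores, might also be read as showing that the decisions were the same. No effect on participants is claimed.

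**Working it through.** There is no planned figure to reproduce: the sample of 8 is described as arbitrary, and no power, margin or effect size is given. The check is a mapping, followed by illustrations.

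**Mapping the primary aim to the plan**

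| Part of the aim | Data item (5.0) | Primary-aim statistic (8.0) | Early-versus-later result? |
|---|---|---|---|
| Same decisions | None; confidence score is a weak proxy | None that fits | No |
| Equally likely to be chosen | Better-quality pick, four readers | Inter-rater kappa | Not planned |

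**Inputs.** From the documents: 4 readers, 8 patients, hence 4 × 8 = 32 quality picks, if all 8 patients are evaluable. The pick and decision patterns below are assumed for illustration.

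**1. Kappa on the quality pick cannot show which scan was preferred.** Fleiss kappa = (P − Pe)/(1 − Pe), where P is mean pairwise agreement and Pe is chance agreement.

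- Later-set picks per patient 4,4,4,4,4,3,3,1, total 27/32 = 84.4%. A unanimous patient contributes 1. A 3–1 split contributes (3×2 + 1×0)/(4×3) = 0.5. P = (5×1 + 3×0.5)/8 = 0.8125. Pe = 0.844² + 0.156² = 0.736. Kappa = (0.8125 − 0.736)/(1 − 0.736) = 0.289, using unrounded values.
- Mirror image 0,0,0,0,0,1,1,3, total 5/32 = 15.6%. P and Pe are unchanged, so kappa is again 0.289.

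Swapping the early and later labels leaves kappa the same.

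**2. Kappa needs raw agreement beside it.**

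- 31/32 (seven patients 4, one patient 3): P = (7 + 0.5)/8 = 0.9375; Pe = (31/32)² + (1/32)² = 0.9395; kappa = −0.03 despite 93.8% pairwise agreement.
- 32/32: Pe = 1, so kappa is undefined.

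**3. Adding a decision field but analysing it only by between-reader kappa would not close the gap.** Suppose the two clinical readers agree fully on each set, with 4 of 8 patients in each of two categories. At each time point observed agreement is 1, chance is 0.5² + 0.5² = 0.50, and Cohen's kappa = (1 − 0.50)/(1 − 0.50) = 1.00. Take early decisions 1,1,1,1,0,0,0,0:

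| Later decisions | Kappa, early | Kappa, later | Early/later match within reader |
|---|---|---|---|
| 0,0,0,0,1,1,1,1 | 1.00 | 1.00 | 0/8 |
| 1,1,0,0,1,1,0,0 | 1.00 | 1.00 | 4/8 |
| 1,1,1,1,0,0,0,0 | 1.00 | 1.00 | 8/8 |

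**4. Precision of a direct early-versus-later proportion, per reader.** Clopper-Pearson 95% limits are the 0.025 quantile of Beta(x, n − x + 1) and the 0.975 quantile of Beta(x + 1, n − x). When x = n the lower limit is 0.025^(1/n).

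| Agreement | Exact 95% interval |
|---|---|
| 8/8 | 0.025^(1/8) = 63.1% to 100% |
| 7/8 | 47.3% to 99.7% |
| 6/8 | 34.9% to 96.8% |
| 6/6 (two patients not evaluable) | 0.025^(1/6) = 54.1% to 100% |

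**The case against.** This is an 8-patient pilot with no power analysis, and even perfect agreement would be compatible with 63.1%, so the fix cannot settle the primary aim. The documents do not say the larger study will be powered on decisions. Inputs to a decision are collected blind to date: post-operative epidural grade and thickness (item g), residual marrow replacement (h) and adjacent-level involvement (j), plus the clinicians' confidence. Several such findings are compared early against late under the secondary aims. The quality picks must be tabulated to calculate kappa, so the later-set share is available from the same table. Finally, isolated reads in random order with a target-matching rule are more than a form change.

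Much of this stands as qualification. The quality-pick point alone is a reporting omission and a smaller matter. Items g, h and j overlap with the level and extent of a target. Reading workflow does change: each clinician would read 8 × 2 = 16 sets singly before comparing them.

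It does not remove the core. Items g, h and j are neuroradiologists' findings, and neither a finding nor a confidence score is a treating clinician's decision. Pilot status excuses the lack of a test or of precision, but not a primary aim whose decision half has no endpoint. A decision not captured at the blinded read cannot be recovered from the listed items; it would need a new read.

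**Conclusion.** The concern holds. Of the two parts of the primary aim, one has no recorded outcome beyond a weak proxy. The other has a paired proxy on quality with no planned early-versus-later summary. The sole primary-aim statistic measures a different quantity, as the identical kappa of 0.289 for opposite preferences shows. The need to correct this before the first blinded read rests on the decision part.

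The mapping rests only on the text of sections 2.0, 5.0, 6.0 and 8.0. The kappa figures rest on invented patterns and illustrate a property of the statistic; they do not predict results. The intervals assume 8 evaluable patients unless stated and apply to one reader at a time.

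**What to change.** **Section 5.0.** The spine surgeon and the radiation oncologist read each date-blinded set separately, in random order, not back to back for the same patient, and before the side-by-side comparison. For each set they record:

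- a management decision, from one common list of categories that the study team writes into the protocol before the first read;
- the intended target, by level and extent, since section 1.0 gives defining the treated area as the purpose of the planning MRI.

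After the comparison they record which set they would use to guide management. The better-quality pick by all four readers stays as a separate item.

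**Section 8.0.** Report:

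1. for each of the two clinical readers, early-versus-later decision agreement as n/N with an exact 95% interval and the full early-by-later table (agreement depends on how coarse the categories are), and target agreement by a matching rule fixed beforehand;
2. for each of these two readers, the proportion choosing the later set to guide management, with an exact 95% interval;
3. for each of the four readers, the proportion picking the later set as better quality;
4. kappa with raw percent agreement for each named item: quality pick (four readers), and set chosen, early decision and later decision (two readers).

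Do not pool readers as if their reads were independent. Label everything descriptive, for planning the larger study.

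The minimum that closes the gap is one decision field per set with n/N agreement, plus the later-set choice proportion.

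**Cost.** No new scans or patients; extra fields for two readers and some descriptive lines. Reading takes longer, by an amount the documents do not allow one to estimate. A reader may recall the first read of a patient, which would inflate agreement; random order and separation reduce this but do not remove it. The intervals stay wide.

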### *Secondary aims:*

Investigate the differences between early and late MRI by comparing:

Size of tumor in three dimensions;

Extent of edema;

Presence and extent of fluid collection;

Spine Oncology Study Group score;

Involvement of adjacent levels;

Progression of tumor;

Patient's preference/performance scale right after each image had taken: level of discomfort (measured by visual analog scale) at around the time (within 48 hours) each MRI was performed.

### *Sample:*

Patients admitted to Cleveland Clinic for surgical management of metastatic extradural spinal tumors will be considered for the study. We anticipate the initial enrollment of 8 patients, which is a number chosen arbitrary for the pilot study. Based on results of this study we will perform power analysis and determine the number of subjects needed to get statistically significant results. Inclusion will not depend in any way on age, gender, ethnicity, or any other personal characteristics other than clinical relevance. We expect the study population to be similar to the spine surgery population seen at the Cleveland Clinic for neoplastic pathologies.

### **3.0 PATIENT/SAMPLE SELECTION**

#### *Inclusion criteria:*

Patients meeting the following criteria will be included to the study:

- Age > 18 yrs;
- Metastatic or primary malignant tumor involving spinal column, with or without extension into the epidural space
- Operated for debulking, decompression or separation surgery;
- An MRI performed within 72 hours after surgery is needed;
- Image quality acceptable for comparison with later MRI as read by a neuroradiologist;
- Karnofsky score of 60 or higher;
- Able to consent for the study.

#### *Exclusion criteria:*

- Any patient who previously underwent spinal surgery at these levels will be excluded to eliminate late postoperative changes.
- Intradural extension of the tumor.
- Patients, whose MRI at post operative 48-72 hours are not readable due to artifacts or disease process shall not be included in the study.
- Patient not able to tolerate MRI scan due to claustrophobia or severe pain or allergic reaction to contrast.
- Patients with a eGFR < or = to 30 will be excluded to avoid issues related to contrast administration in such patients. This GFR threshold cutoff level is chosen per institutional policy, because below that level other measures would be required (hydration or no contrast administration). In order to keep the imaging information as uniform as possible in such a small study group, patients with a low GFR will not be enrolled in the study.

### **4.0 REGISTRATION PROCEDURES**

Since this is a non-therapeutic trial, summary information for monthly accrual will be entered into the Oncore database.

### **5.0 RESEARCH PLAN**

#### *Imaging protocol:*

We will identify the patients meeting the above criteria and consent them for the study. Another MRI will be obtained 2-3 weeks postoperatively. The routine spine MRI protocol will be utilized, which includes the following sequences: haste localizer, sagittal T1, T2, and STIR, axial T2 for lumbar spine or axial gradient echo for cervical and thoracic spine, axial T1, post contrast sagittal and axial T1. All scans will be obtained using a 1.5 Tesla magnet. When indicated, sedation or anxiolysis and IV hydration for low glomerular filtration rate will be administered by radiology per protocol.

*Image analysis:*

The image acquisition dates will be blinded and the images independently reviewed by two neuroradiologists, a radiation oncologist, and a spine surgeon. Each of them will compare and choose a better-quality image. These results will be compared and inter-observer variability will be established.

Radiology (2 independent neuro-radiologists) will be blinded to all quantitative data (including the date of post-op MRI) and they will be asked to evaluate the following parameters:

- a. Level(s) of surgery = number ie L3, L4
- b. Presence of hardware = Y or N
- c. Does hardware obscure canal = Y or N
- d. Nature of surgery = 0 separation surgery/decompression only, 1 corpectomy, 2 combination of 0+1
- e. Fluid collection = AP\*Lateral\*CC in CM
- f. Epidural disease pre op = SOSG grading system AND max thickness at N level
- g. Epidural disease post op = SOSG grading system AND max thickness at N level
- h. Nature of marrow replacement (preop and residual on post op) = 1-4 for 25%, 50%, 75%, and 100% replaced respectively
- i. Compression fracture pre and post = Y or N
- j. Adjacent level involvement pre and post = Y or N

Spine surgeon and radiation oncologist will be blinded to date and use a scale of

- a. 0 = not confident,
- b. 1 = confident
- c. 2 = very confident

in terms of confidence in contouring/tumor targeting using a particular image set

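### The late MRI is timed only from surgery and its window lies inside the typical radiosurgery window, so a compliant late scan can follow SRS without the plan ordering or identifying such pairs

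*Combined protocol and SAP*

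**What the plan says.** **Late scan.** The Imaging protocol in section 5.0 states "Another MRI will be obtained 2-3 weeks postoperatively". The table in section 6.0 repeats that window. Neither mentions radiation.

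**Radiosurgery.** Background and significance in section 1.0 states "SRS is typically scheduled two-to-four weeks after the surgical procedure". It also gives MRI a role before treatment: "Planning phase of SRS includes imaging of the surgical bed in the form of MRI so as to delineate the precise area to be radiated". It adds that a study of brain metastases "has supported obtaining MRI as close to SRS as possible". The same section says that the team's current practice is to image 48 to 72 hours after surgery.

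**What the two scans are compared for.** The hypothesis is that late imaging "is no worse in quality and utility than immediately postoperatively". The primary aim asks whether the late scan leads to the same decisions and "has the same probability of being chosen by a physician for guiding the subsequent management of the patient". The secondary aims compare, among other things, tumor size, edema and "Progression of tumor".

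**Analysis and use.** Section 8.0 plans kappa for inter-rater reliability on the primary aim and descriptive statistics for the secondary aims. The Sample paragraph in section 2.0 says: "Based on results of this study we will perform power analysis and determine the number of subjects needed to get statistically significant results".

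**What is absent.** The eligibility criteria, imaging and reading plan, parameter table and statistics section do not require the late scan to precede SRS. They do not list an SRS date, and they do not say how a pair would be handled if its late scan followed SRS.

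**The concern.** The study asks whether a later scan can take the place of an early one in deciding what to do next. For many such patients the next step may be SRS, and the background describes MRI as part of SRS planning. The question is therefore clearest when both scans precede treatment. The timing rule does not secure this, because it counts days from surgery and takes no account of when radiation is given.

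Two things are at stake for a pair whose late scan follows SRS:

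- **Utility.** That scan could not have guided the SRS already delivered. It says less about guiding subsequent management than a pre-treatment scan would.
- **Interpretation.** An early-late difference in tumor size, edema or progression could reflect elapsed time, treatment, or both. Only the late scan is exposed to this.

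The study is a pilot whose results are to inform a larger study, so a scheduling gap left open here could be carried forward.

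**Working it through.** The plan states no figure on this point. Enrollment of 8 is described as arbitrary and no power analysis was done, so the check compares windows.

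**Inputs**

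- Early MRI: within 72 hours, so by day 3 (section 3.0, Inclusion criteria).
- Late MRI, M: days 14-21 (sections 5.0 and 6.0).
- SRS, S: typically days 14-28 (section 1.0). The word typically makes this range approximate.
- Share of patients receiving SRS: not stated. SRS is not an entry requirement in section 3.0.

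**Step 1: overlap.** [14, 21] lies wholly within [14, 28]. Any late scan after day 14 can follow SRS and still comply.

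**Step 2: which scan is exposed.** The early scan is done by day 3, and the SRS window opens on day 14, 14 − 3 = 11 days later. Within the typical window only the late scan can follow SRS.

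**Step 3: can SRS go ahead without the late scan?** Yes. Current practice already supplies an MRI at 48 to 72 hours, so treatment need not wait for the study scan.

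**Step 4: bounds on the share of SRS recipients affected, P(S < M).**

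- If SRS is always on day 21 or later: 0%.
- If SRS is always on day 14 and the MRI is later: 100%.
- Longest SRS-to-MRI gap within the windows: 21 − 14 = 7 days.

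The documents do not narrow this range.

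**Step 5: illustrations only, with assumed dates.**

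| Assumption | Formula | P(S < M) |
|---|---|---|
| M and S independent and uniform on their windows | E[(M − 14)/14] = 3.5/14 | 25% |
| M fixed at 14, 17.5 or 21; S uniform | (M − 14)/14 | 0%, 25%, 50% |
| S fixed at 14, 17.5 or 21; M uniform | (21 − S)/7 | 100%, 50%, 0% |

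In whole days there are 8 × 15 = 120 compliant combinations. SRS comes first in 0 + 1 + … + 7 = 28 of them (28/120 = 23%), and 8 more fall on the same day (36/120 = 30% in all).

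Under the 25% illustration with 8 patients, the chance of at least one affected pair depends on the assumed share receiving SRS:

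- All: 1 − 0.75^8 = 90%, with 8 × 0.25 = 2.0 pairs expected.
- Half: 1 − 0.875^8 = 66%, with 1.0 expected.
- A quarter: 1 − 0.9375^8 = 40%, with 0.5 expected.

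One pair is 1/8 = 12.5% of the planned sample. Independence of the two dates is doubtful, since the background links MRI to SRS planning. These figures show that the situation is possible in a sample this small; they do not estimate how often it will occur.

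**The case against.** The best reply is that purpose settles the order. Postoperative imaging is meant to guide further therapy, the primary aim concerns later management, and the surgeon and radiation oncologist rate their confidence in contouring. A scan after SRS would defeat the team's own aim, so what is missing is an unstated rule and nobody plans to scan after treatment. This is fair as to intent. But intent does not schedule the scan, and current practice gives SRS no reason to wait for it.

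A second reply is that no planned result fails. The reviewers judge image sets with dates hidden, and the plan does not measure whether a scan actually guided treatment. There is no test or decision rule. This stands: the preference and confidence ratings remain usable, and the weakness lies in what a post-SRS scan can say about utility and in the descriptive secondary measures.

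A third is that the documents do not say radiation alters the MRI within the 7 days at most that the windows allow. This also stands, and it is why the size is left as unknown.

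Some stronger inferences should be resisted:

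- A reader might infer that the SRS date will not be recorded. The documents only fail to list it. No case report form is included, and the section 6.0 table also omits the planned discomfort scale, so it is not a full data list.
- A reader might infer that the exclusion criteria set a general uniformity standard which radiation breaches. The uniformity remark explains the low-GFR exclusion and concerns contrast. The prior-surgery exclusion concerns history before the study.
- A reader might take 25% as the expected share of affected pairs. It follows only from assumed dates.

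**Conclusion.** The point holds as a limited one worth considering. For patients who receive SRS, the stated timing rule permits a late scan that could not have guided that treatment, and the documents neither prevent nor identify such pairs. This weakens those pairs as evidence on the primary aim, and their size, edema and progression measures could combine time with treatment on the late side only.

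The frequency cannot be known from the documents (0 to 100% of SRS recipients, whose number is unstated), nor can the size of any radiation effect on the image. Patients without SRS are unaffected. The conclusion rests on reading the stated weeks as days 14-21 and 14-28, and on the SRS range being typical, not fixed.

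A reader might go further and conclude that the primary comparison or the kappa is biased. The documents do not support that: no effect on the blinded ratings or on rater agreement is shown. Nor do they say how the secondary measures would enter the later power analysis, so an error in sizing the larger study is a possibility only.

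**What to change.** - **Section 5.0, Imaging protocol.** Add a rule such as: *The late study MRI is to be done on days 14 to 21 after surgery and before any radiation to the operated level, provided this does not delay treatment.*
- **Data items.** Record the date of first radiation to the operated level.
- **Section 8.0.** Keep all pairs in the main early-late comparison, identify any pair whose late scan followed radiation, and also show the descriptive results without those pairs.

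The cost is a slight scheduling constraint, one extra chart date and one reporting sentence. The proviso protecting treatment means some post-radiation scans may still occur, which is why the date and the second display are needed. With 8 patients, the display without those pairs is for transparency; it will not measure a radiation effect.

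### The primary aim concerns which scan a physician would choose to guide management, but the only choice recorded is a date-blind pick on image quality, so scan age formally enters no choice.

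*Combined protocol and SAP*

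**What the plan says.** Section 2.0 (Primary aim) has two parts: whether the later MRI leads to the same clinical decisions, and whether it "has the same probability of being chosen by a physician for guiding the subsequent management of the patient" as the early one. This point concerns the second part. The hypothesis in section 1.0 likewise names utility alongside quality.

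Section 5.0 describes what the readers do. "The image acquisition dates will be blinded and the images independently reviewed by two neuroradiologists, a radiation oncologist, and a spine surgeon", and "Each of them will compare and choose a better-quality image". The blind is stated again for the neuroradiologists' list of parameters and for the clinicians' score: "Spine surgeon and radiation oncologist will be blinded to date and use a scale of" 0 to 2 "in terms of confidence in contouring/tumor targeting using a particular image set". No later step reveals the dates.

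Section 1.0 (Background and significance) says that "SRS is typically scheduled two-to-four weeks after the surgical procedure". It also cites a study in brain metastasis that "has supported obtaining MRI as close to SRS as possible". Section 6.0 schedules only the three MRIs, and no SRS date or scan-to-SRS interval is listed for collection. For the primary aim, section 8.0 plans kappa for inter-rater reliability.

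**The concern.** A physician who picks a scan to guide treatment normally knows when each scan was taken, and the study's subject is the timing of that scan. Here the readers choose on quality, without dates, and the result stands in for a choice about management. Two differences are folded together: the question asked (quality rather than management) and the information available (dates hidden rather than known).

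If the two scans are picked about equally often on quality, the natural report would be that they are equally likely to be chosen for management. The data would not show that. The pilot is meant to inform a larger study, so the mismatch could carry forward. It also cannot be repaired in analysis, because the management choice was never collected.

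**Working it through.** The plan gives no figure to reproduce: the sample of 8 is described as arbitrary, and no margin, error rate or power is stated. The check has four steps.

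**1. Reader outputs against the aim (section 5.0 against section 2.0).**

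| Output | Readers | Date known? | Asks which scan would guide management? |
|---|---|---|---|
| Pick of the better image | All four | No | No |
| Confidence score, 0 to 2 | Surgeon, radiation oncologist | No | No |
| Radiological parameters | Two neuroradiologists | No | No |

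No row answers the second part of the primary aim directly.

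**2. Size of the age difference that is withheld.** Inputs, in days after surgery: early scan 0 to 3 (within 72 hours, section 3.0); late scan 14 to 21 (section 5.0); SRS 14 to 28 (section 1.0, given as typical).

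- Within-patient gap, late day minus early day: 14 − 3 = 11 to 21 − 0 = 21 days.
- Age of the early scan at SRS: 14 − 3 = 11 to 28 − 0 = 28 days.
- Age of the late scan at SRS: 14 − 21 = −7 to 28 − 14 = 14 days. The negative end means that the stated windows allow a late scan up to 7 days after SRS.

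The paired gap of 11 to 21 days is the relevant figure, because both scans come from the same patient.

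**3. What an even split can show.** Let p(Q) be the probability that the late scan is picked on quality when blind, p(M) the probability that it is chosen for management when blind, and p(D) the same with dates known. The plan observes only p(Q). The two gaps are:

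- p(M) − p(Q): the effect of changing the question.
- p(D) − p(M): the effect of showing the dates.

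The planned data estimate neither gap, so p(Q) = 0.5 does not imply p(M) = 0.5 or p(D) = 0.5. For context on precision, one reader picking the late scan in 4 of 8 patients has an exact (Clopper-Pearson) 95% interval of 0.157 to 0.843.

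**4. Direction.** Section 1.0 points both ways. One cited study favours imaging close to SRS. Earlier brain-tumor work is cited as treating imaging in the first 72 hours as indispensable for radiotherapy planning, and the team's present practice is MRI at 48 to 72 hours. The sign of p(D) − p(M) cannot be derived from this.

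**The case against.** The strongest defence is that the blind is deliberate and sound. It stops readers from choosing by belief about timing, which is the matter under study. A choice made with dates known could largely return those beliefs. Section 1.0 states the goal of the imaging in terms of image quality, so reading the aim as the image preferred on its merits is defensible. This stands: the blind should stay, and an unmasked choice should not become the main result.

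Other limits also stand:

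- Edema, blood and serum on early scans may let a reader guess the order. Scan age could therefore leak in, informally and unmeasured.
- Contouring confidence is more than appearance and lies close to the treatment-planning task.
- Age at SRS matters only for patients who go on to SRS, and section 3.0 also admits debulking and decompression.
- This is a pilot of 8 with no inferential claim about choice.

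A reader might infer that physicians who knew the dates would mostly choose the later scan, so that the blinded result hides a preference for it. The documents do not support this: the background cites evidence and current practice on both sides, and any figure for the shift would only restate an assumption about behaviour. If dates did favour only the late scan, the no-worse hypothesis would be strengthened and only the same-probability wording would suffer.

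None of this supplies the missing management choice. The merits-only reading still needs someone to be asked which scan they would use.

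**Conclusion.** The concern holds in limited form. The second part of the primary aim is about a choice to guide management, and the plan collects only a date-blind quality choice and a date-blind confidence score. Scan age, which differs by 11 to 21 days within a patient, formally enters neither. An even split on blinded quality would not establish an equal probability of being chosen for management.

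The direction and size of any difference once dates are known are not determinable from the documents. It would also be too strong to say that blinding is an error or that timing cannot influence a reader at all. The 11-to-21-day figure rests only on the stated scan windows; the ages at SRS also assume the typical SRS timing and apply only to patients who receive it. No sample-size or error-rate figure is affected.

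**What to change.** Keep the blinded quality choice and confidence scores as planned. For the surgeon and the radiation oncologist, add:

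1. Still blind, one question: which scan would you use to guide management (scan A, scan B or either)? Lock the answer.
2. Then show both scan dates and, for patients going to SRS, the planned or actual SRS date. Record the same choice again. This requires the SRS date to be collected.

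Report three results under their own names. The blinded quality choice is image quality. The blinded management choice is the masked answer to the second part of the primary aim. The date-known choice is a separate supportive result, given per clinician, with a statement that it is open to expectation and to anchoring on the locked answer.

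If the question is not added, limit the primary conclusion to blinded image quality and contouring confidence.

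The cost is up to two short questions per patient for two existing readers: 2 × 2 × 8 = 32 answers at most, with no extra scans. The downside is an unmasked result that must be read with caution.
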